## 6.2.1 Masking Procedures

The study subject and the outcomes assessor will be masked to treatment assignment. However, the surgeon will not be masked to the treatment assignment, since s/he must know what procedure to perform.

In order to ensure the outcomes assessor is masked, s/he will not be present at the surgical site, and s/he will not have access to data from the baseline and surgical visit. However, because one procedure involves a full-thickness incision and the other does not, we expect that the outcomes assessor will be able to determine which procedure many of the patients received through visual inspection. Thus, we will use photographs as a backup to verify the outcomes reported, by holding cardstock to cover the skin incision scar in the photographs so that evidence/lack of an incision is not visible.

## 6.3 Assessment of Clinician and/or Subject Compliance with Study Procedural Intervention

The Project Director will regularly monitor surgical activities in-person to ensure that the surgeons are following the study procedures and are performing the correct procedure. After each surgical outreach period, the Coordinating Center (CC) will compare the assignment reported on the Surgical Evaluation form against the actual assignment.

## 6.4 **Procedures for Training of Clinicians on Procedural Intervention**

6.5 [name] will train up to two Ethiopian surgeons (ophthalmologist and IECW) in how to perform the BRAP procedure. Then [name] and the Ethiopian surgeons will review/discuss the Trabut procedure steps to ensure that they both plan to perform the procedure in the same way. [name] will monitor the surgeries to

#### ensure that all surgeons are performing the two procedures in the same way.Procedures for Ensuring BRAP Surgery is Performed According to Study Procedure

- 1) We will provide the study surgeon with professional sketches of the surgery procedure, and [name] will review these steps with him. The surgeon will take these sketches with him to the surgery site each time he performs the BRAP procedure.
- 2) [name] will be present for the first two surgery recruitment periods. She will observe the study surgeon closely to ensure all steps of the procedure are understood and being followed. Once he is performing all steps independently and consistently, she will periodically observe his surgery, but she will continue to examine each patient at the end of surgery to ensure that the surgery was performed according to the study procedure.
- 3) After two surgical periods, if [name] is comfortable with the study surgeon performing surgery in her absence, the surgeon may proceed to perform study surgeries independently. At the start of each surgery period, he will review the surgical sketches to refresh his memory on the surgical approach and will be encouraged to have the project manager communicate with [name] to address any questions or concerns.
- 4) In [name] absence, a second individual will be present at the surgery site to review completed surgeries and ensure the suture and incision placement follow the protocol.
- 5) Each week that study surgeries are performed in [name] absence, images of the eyelid immediately after surgery will be uploaded to the study's secure shared folder. [name] will review each image to ensure that there are no systematic differences from the study procedure.
- 6) If systematic differences are noted, [name] will contact the project manager and study surgeon to discuss and address them.

#### 6.6 Study Procedural Intervention Description

Surgeons will receive the surgical procedure assignment just prior to surgery for that participant. Immediately before beginning surgery, the surgeon will confirm with the surgical assistant whether the procedure is BRAP or Trabut.

## 7. STUDY DISCONTINUATION, PARTICIPANT DISCONTINUATION OR WITHDRAWAL

In this trial, all subjects will receive repeat trichiasis surgery using the BRAP or Trabut procedure. The primary study intervention is surgical procedure, with either Trabut or the newly developed BRAP procedure being performed.

## 7.1 Subject Withdrawal

Subjects may withdraw voluntarily from the study at any time. Because the intervention is a one-time intervention, the investigators should not have reason to withdraw a study subject for non-compliance.

## 7.2 Lost to Follow-Up

If a participant misses a follow-up visit, the outcome examiner will make arrangements with the Community Health Worker for the two of them to visit the patient's village and home together on one of the 'mop up' days.

If evaluation for a required visit is not completed within the visit window, a Missed Visit form should be completed at the close of the window and submitted with the relevant blank follow up form. At least three attempts should be made to find the participant within the relevant window before a Missed Visit form is completed. If the participant has died, the form can be completed immediately. If the participant has relocated somewhere in the district, efforts should be made to track him/her at the new location. The participant is still eligible for any subsequent visits.

## 8. STUDY ASSESSMENT PROCEDURES

#### 8.1 Efficacy Assessment

This section lists the procedures and describes the general approach for data collection.

Ocular Examination: The ocular exam will consist of a detailed evaluation of each eyelid. This information will be collected on the day of surgery. At each follow up study visit, the study eye will be assessed for the presence of *repeat* post-operative trichiasis, eyelid contour abnormality and granuloma.

Visual Acuity: Visual acuity will be assessed monocularly at baseline and will be assessed again at the post-operative 3-6 months and 12 months visits; it will be assessed using an Early Treatment of Diabetic Retinopathy (ETDRS) tumbling "E" chart on a smartphone, using the PEEK acuity app.

Trichiasis Surgery: All participants will receive trichiasis surgery with either the BRAP or Trabut procedure.

Photographs: Photographs will be taken of the full face (headshot) and of each eyelid preoperatively, during surgery, immediately postoperatively, and at each follow up visit.

#### 9. STATISTICAL CONSIDERATIONS

#### 9.1 Study Hypotheses

#### Primary Aim:

#### Null hypothesis:

1) Surgery performed using the Bevel/rotate/advance procedure (BRAP) will have the same rate of post-operative trichiasis as surgery performed using the Trabut procedure.

#### Alternative hypothesis:

1) Surgery performed using the BRAP procedure will result in a relative 30% reduction in the rate of post-operative trichiasis compared to surgery using the Trabut procedure.

#### Secondary Aim:

#### Null hypothesis:

1) Eyelids operated with the bevel/rotate/advance procedure will have the same rate of moderate/severe eyelid contour abnormalities rate as eyes operated with the Trabut procedure.

#### Alternative hypothesis:

1) Eyelids operated with the bevel/rotate/advance procedure will have fewer moderate/severe eyelid contour abnormalities than eyelids operated with the Trabut procedure.

#### 9.2 Sample Size Considerations

The planned sample size for this trial is 700 participants. This sample size will give sufficient power to detect a 30% relative difference in post-operative trichiasis rates between the BRAP and Trabut procedures. This estimate is based on the following assumptions:

- 35% of eyelids in the Trabut group will develop post-operative trichiasis during the 12 months following surgery
- Two-sided alpha error = 5%
- Power = 80%
- 10% loss to follow up

In the event that the number of participants is lower than anticipated, we are still adequately powered to detect a clinically significant difference (see table below). For instance, if only 600 participants enroll, we have 80% power to detect a relative difference of 32%.

	Relative Risk							
Number of Participants	1.2	1.3	1.32	1.4	1.5			
560	44%	72%	77%	91%	99%			
600	47%	75%	80%	93%	99%			
640	49%	77%	82%	94%	99%			
720	53%	82%	86%	96%	99%			
800	56%	85%	89%	97%	99%			

Power to Detect a Difference between Treatment Groups

The subset of 186 participants who enrolled and received surgery prior to August 1, 2019 will be excluded from the primary analysis because they were operated prior to precise standardization of the incision and suture placement. These individuals will continue to be followed and cared for in the same manner as all other study participants.

## 9.3 Analysis Plan

We will follow these general analysis principles:

- The primary analyses will be performed according to the participant's assigned intervention (intention-to-treat).
- All participants who complete randomization after August 1, 2019 and have surgery performed will be included in analyses.
- All events following surgery will be counted.
- All analyses will be conducted at the eye level, using the generalized estimating equations approach to correct standard errors (to account for the correlation between two eyes of a subject).

We will use logistic regression analysis for each of the outcomes. In previous trials, we have created time-to-PTT models using Cox proportional hazards with PTT as the outcome. However, with the limited number of follow-up visits, Cox proportional hazards models do not provide much additional information. Hence, we do not plan to conduct such modeling for this trial.

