#### Eyelid Contour Abnormalities

We will evaluate eyelid contour abnormalities at each post-operative visit. The examiner will grade the presence of abnormality using the definition provided below in the statistical considerations chapter. Both field and photographic grades will be utilized. The field grade will serve as the primary grade for the primary study analyses; secondary analyses will utilize the photograph grade. Examiners will be standardized at

the start of the 3-6 month visits. For primary analyses, the eyelid contour grade at 12 months will be used.

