## Post-operative Trichiasis Analyses:

The **primary analysis** will be based on the dichotomous outcome: presence or absence of post-operative trichiasis noted at any time point beginning with the 3-6 month visit and within 12 months following surgery (trichiasis noted at either the 3-6 month or 12

month visit will be considered as post-operative trichiasis, regardless of whether there is trichiasis at the final visit). Both unadjusted and adjusted analyses will be performed. Adjusted analyses will account for the severity baseline PTT, with severity defined based on the table below.

Trichiasis Severity Classification	Description
Mild	1-4 Eyelashes touching globe, no epilation
	OR
	< 1/3 of eyelid epilated, no lashes touching globe
Moderate	5-9 Eyelashes touching globe, no epilation
	OR
	1-4 lashes touching globe and < 1/3 of eyelid epilated
Severe	5-9 Eyelashes touching globe and 1-10 eyelashes epilated
	OR
	10+ Eyelashes touching globe, regardless of epilation status
	OR
	>1/3 of eyelid epilated, regardless of lashes touching

(Gower et al. 2013. JAMA Ophthalmol.;131(3):294-301.)

**Multiple secondary analyses** of post-operative trichiasis will be performed. We will compare the severity of post-operative trichiasis between groups, with severity defined using the table above. Additionally, we will assess the frequency of overcorrection performed at the one-day visit.

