## Eyelid Contour Abnormalities:

**Primary analysis** of eyelid contour abnormalities will be based on a dichotomous variable: presence or absence of moderate/severe contour abnormality at the final study

visit (12 months) using the field grade, which will be based on the definitions below. For the purposes of this analysis, mild will be combined with "no abnormality" and moderate and severe will be combined to form the "moderate/severe contour abnormality" group. We will adjust for first procedure performed (Trabut or BRAP) and severity of pre-operative trichiasis.

Abnormality	Definition
Mild	Vertical deviation from the natural contour, 1 mm in height (less than half the pupil height in daylight) and affecting 1/3 of horizontal eyelid length
Moderate	Vertical deviation from the natural contour 1–2 mm in height (about the pupil height in daylight) or affecting 1/3–2/3 of horizontal eyelid length
Severe	Vertical deviation from the natural contour 2 mm in height (more than the pupil height in daylight) or a defect >2/3 of the horizontal eyelid length

(Gower et al. 2012 PLoS Negl Trop Dis 6(6): e1713)

**Secondary analyses** will explore the relationship between procedure and the full range of eyelid contour abnormalities, which will require use of the photographic grade that will be graded centrally.

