#### Treatment of Missing Data

We have had great success in our trials to date, reporting over 95% follow up at 1 year after surgery in each of our prior trials. However, invariably, some participants will be lost to follow up. To this end, we will conduct sensitivity analyses treating all missing data as success and then as failures. Given that we collect limited external information on this population, it would be difficult to impute the values.

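### Does leaving the 186 participants operated before 1 August 2019 out of every specified analysis undermine the trial's conclusions?

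*Combined protocol and SAP*

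**What the plan says.** Section 9.2 (Sample Size Considerations) states: "The subset of 186 participants who enrolled and received surgery prior to August 1, 2019 will be excluded from the primary analysis". The reason given is that these operations came before incision and suture placement had been standardised. It adds: "These individuals will continue to be followed and cared for in the same manner as all other study participants".

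Section 9.3 (Analysis Plan) lists general principles for all analyses. The primary analyses go by assigned arm, as intention-to-treat. On the population it says: "All participants who complete randomization after August 1, 2019 and have surgery performed will be included in analyses". It then names logistic regression for each outcome.

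The outcome-specific parts of 9.3 do not restate a population. The only sensitivity analyses described concern missing outcomes: "we will conduct sensitivity analyses treating all missing data as success and then as failures". Section 3.5 also uses the word primary for a secondary endpoint: "For primary analyses, the eyelid contour grade at 12 months will be used".

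Section 4.1 gives up to 936 participants randomised 1:1. Section 9.2 gives a planned size of 700.

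**The concern.** Three things invite the criticism.

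- The 186 were already randomised, since Section 6.2 places randomisation on the day of surgery. Removing them sits awkwardly beside an intention-to-treat label.
- Section 9.2 limits the exclusion to the primary analysis, while 9.3 speaks of analyses in general. A reader could ask which set serves contour abnormality, granuloma and 3-6 month PTT.
- The 186 are followed for 12 months, yet no described analysis uses them, so the plan offers no check on whether the result depends on the cut-off.

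If the exclusion were related to arm or outcome, the primary comparison could be biased. If it cost too many participants, the trial would be underpowered. If the population for secondary outcomes were truly open, it could be chosen after the results were known.

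**Working it through.** **1. The plan's own sample size.** Inputs from Sections 9.1 and 9.2: p1 = 0.35, p2 = 0.35 × 0.70 = 0.245, two-sided alpha 5%, power 80%, 10% loss. With p̄ = 0.2975,

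n per arm = [1.960 √(2 p̄(1 − p̄)) + 0.842 √(p1(1 − p1) + p2(1 − p2))]² / (p1 − p2)² = 296.4, so 297.

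The continuity correction (n/4)(1 + √(1 + 4/(n × 0.105)))² gives 315.2, so 316 per arm and 632 in total. Then 632/0.90 = 702.2, rounded up to 703, against 700 stated. The plan's figure reproduces.

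**2. What the exclusion leaves.** 936 − 186 = 750, which exceeds 700. The excluded share is 186/936 = 19.9%. Because 936 is a maximum, this is a lower bound; with 700 + 186 = 886 randomised it is 21.0%. Power uses the two-proportion formula without continuity correction, one eye each and 10% loss:

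| Participants analysed | Evaluable per arm | Power, 35% vs 24.5% |
|---|---|---|
| 700 | 315.0 | 82.3% |
| 750 | 337.5 | 84.9% |

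The analysis is by eye. Taking 31/23 = 1.35 eyelids per participant (Section 3.2) and an assumed between-eye correlation of 0.8 down to 0.3, power at 750 is 83.2% to 89.8%. The 1.35 is rough: it divides eyelids assessed by patients operated in a small non-trial series.

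**3. Scope for secondary outcomes.** The restriction in 9.3 stands among the general principles, carries no primary or secondary qualifier, and is followed by the model for each outcome. Read that way, it covers every outcome. Section 9.2 is narrower but does not place the 186 in any other analysis. The two statements are compatible: 9.2 explains the exclusion where sample size is discussed, and 9.3 sets the population. Because randomisation and surgery fall on the same day, the surgery date in 9.2 and the randomisation date in 9.3 mark the same boundary. Only 1 August itself is unassigned (before in one section, after in the other).

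**4. Dependence on the cut-off.** Illustration on expected counts: logit(PTT) = arm + period, 337.5 later and 83.7 early evaluable per arm, one eye each, Trabut 35% in both periods. All early-period differences are assumed. A positive value favours BRAP.

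| Later difference | Early difference | Set | OR (95% CI) | p |
|---|---|---|---|---|
| 10.5 (planned) | – | later only | 0.60 (0.43–0.84) | 0.003 |
| 10.5 | 0 | all | 0.67 (0.50–0.90) | 0.008 |
| 8.0 (assumed) | – | later only | 0.69 (0.50–0.95) | 0.025 |
| 8.0 | −5 | all | 0.78 (0.58–1.04) | 0.093 |
| 8.0 | 0 | all | 0.74 (0.56–1.00; upper limit 0.995) | 0.046 |
| 8.0 | +4 | all | 0.72 (0.53–0.96) | 0.024 |
| 8.0 | +8 | all | 0.69 (0.51–0.92) | 0.012 |

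At the planned 10.5 points, the all-participant result loses significance only when the early difference is about −10.8 points (−10.0 to −13.1 over the eye-level range in step 2). With no early difference, the two sets disagree on significance only when the later difference lies between about 7.0 and 7.9 points.

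**5. What the early data could add.** For the early cohort alone, the 95% half-width is 1.96 √((0.35 × 0.65 + 0.245 × 0.755)/83.7) = 13.8 points. An arm-by-period interaction would have 80% power only for a change of 20 to 22.5 points. Simple pooling of 936 would have power 91.7% if the early relative reduction were also 30%, 84.9% if it were 15%, and 75.4% if it were nil, against 84.9% for the later cohort alone.

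**The case for a change.** The strongest case for a change is that a supportive analysis of everyone randomised is cheap, uses data already collected, and is more credible if specified in advance. For a moderate effect the choice of set can matter. With an 8-point later difference and BRAP 5 points worse early, p moves from 0.025 to 0.093. Under the missing-data rules in 9.3, with no early difference, it moves from 0.028 to 0.051 (missing as success) and from 0.042 to 0.070 (missing as failure). The timeline in Section 1.1 also places 3-6 month visits in June to August 2019, so some early outcomes could have existed around the cut-off date.

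Part of this stands. No section specifies an analysis of the 186, the scopes of 9.2 and 9.3 differ in wording, and a descriptive account of the early cohort by arm would be useful to readers. The rest is weaker. The 8-point scenario is not a figure from the plan, and the loss of significance needs an assumed null or harmful early effect; favourable early effects leave p below 0.05. The small uncontrolled series in Section 3.2 pointed in BRAP's favour, though it is too small to lean on. A pooled analysis would also answer a different question, mixing surgery before and after standardisation. Nothing in the document shows that outcomes by arm were seen when the date was set, so that remains a question and is no evidence of bias. Section 13 promises a de-identified dataset. It does not say whether the 186 are in it, so it softens the worry about checking without removing it.

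**Conclusion.** No change to the plan is needed. The exclusion is by calendar date, is the same for both arms and has a stated technical reason, so the participants randomised afterwards form a valid comparison by assigned arm. Between 700 and 750 remain, with 82.3% to 84.9% power on a one-eye basis, against the 80% planned. The adverse-event provisions in Sections 4.4 and 12.1.2 carry no date limit, so safety oversight still covers the 186.

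The mismatch between 9.2 and 9.3, including the unassigned 1 August, is a drafting slip that an analyst would resolve by applying the general principle in 9.3 to every outcome. The early cohort can be described in the trial report without any change to the analyses specified. Giving up at least 19.9% of randomised participants in return for a comparison of standardised procedures is a fair trade-off. Adding them back could raise power to 91.7% or lower it to 75.4%, depending on an early effect that nobody can know in advance.

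The conclusion rests on an even split between arms, equal 10% loss, a Trabut rate of 35%, and a cut-off set without knowledge of results by arm. The document does not contradict the last of these, but does not state it either.

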## Post-operative Trichiasis Analyses:

The **primary analysis** will be based on the dichotomous outcome: presence or absence of post-operative trichiasis noted at any time point beginning with the 3-6 month visit and within 12 months following surgery (trichiasis noted at either the 3-6 month or 12

month visit will be considered as post-operative trichiasis, regardless of whether there is trichiasis at the final visit). Both unadjusted and adjusted analyses will be performed. Adjusted analyses will account for the severity baseline PTT, with severity defined based on the table below.

Trichiasis Severity Classification	Description
Mild	1-4 Eyelashes touching globe, no epilation
	OR
	< 1/3 of eyelid epilated, no lashes touching globe
Moderate	5-9 Eyelashes touching globe, no epilation
	OR
	1-4 lashes touching globe and < 1/3 of eyelid epilated
Severe	5-9 Eyelashes touching globe and 1-10 eyelashes epilated
	OR
	10+ Eyelashes touching globe, regardless of epilation status
	OR
	>1/3 of eyelid epilated, regardless of lashes touching

(Gower et al. 2013. JAMA Ophthalmol.;131(3):294-301.)

**Multiple secondary analyses** of post-operative trichiasis will be performed. We will compare the severity of post-operative trichiasis between groups, with severity defined using the table above. Additionally, we will assess the frequency of overcorrection performed at the one-day visit.

## Eyelid Contour Abnormalities:

**Primary analysis** of eyelid contour abnormalities will be based on a dichotomous variable: presence or absence of moderate/severe contour abnormality at the final study

visit (12 months) using the field grade, which will be based on the definitions below. For the purposes of this analysis, mild will be combined with "no abnormality" and moderate and severe will be combined to form the "moderate/severe contour abnormality" group. We will adjust for first procedure performed (Trabut or BRAP) and severity of pre-operative trichiasis.

Abnormality	Definition
Mild	Vertical deviation from the natural contour, 1 mm in height (less than half the pupil height in daylight) and affecting 1/3 of horizontal eyelid length
Moderate	Vertical deviation from the natural contour 1–2 mm in height (about the pupil height in daylight) or affecting 1/3–2/3 of horizontal eyelid length
Severe	Vertical deviation from the natural contour 2 mm in height (more than the pupil height in daylight) or a defect >2/3 of the horizontal eyelid length

(Gower et al. 2012 PLoS Negl Trop Dis 6(6): e1713)

**Secondary analyses** will explore the relationship between procedure and the full range of eyelid contour abnormalities, which will require use of the photographic grade that will be graded centrally.

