## 3.3 Potential Risks and Benefits

## Potential Risks

The risks associated with this study are minimal. Repeat surgery to treat post-operative trichiasis is a standard practice commonly performed in many countries, and all subjects enrolled in this study would be offered repeat surgery regardless of whether they participate in the clinical trial. Theoretically, a newly-developed procedure utilizing a new method for repositioning lashes could ultimately be found to have higher rates of post-operative trichiasis or eyelid contour abnormalities. Preliminary data suggest that this new procedure is not associated with an increased risk of eyelid contour abnormalities or of higher post-operative TT rates. However, it is important to be aware of this possible risk.

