#### **OBJECTIVES AND ENDPOINTS**

#### 3.4 Study Objectives

This study has one primary objective:

1) To determine whether the rate of post-operative trichiasis (PTT) differs significantly at 12 months after repeat surgery with the Trabut procedure compared to surgery performed with a recently developed procedure, the bevel/rotate/advance procedure (BRAP).

This study has three secondary objectives:

- 1) Determine whether the frequency of moderate/severe eyelid contour abnormalities at 12 months after surgery differs between the two procedures.
- 2) Determine whether the frequency of pyogenic granulomas within 12 months after surgery differs between the two procedures.
- 3) Determine whether the frequency of PTT differs between the two procedures at 3-6 months after surgery.

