#### 6.1.2 **BRAP**

#### **Beveled Incision**

[figure not shown]
A Trabut plate is used to evert the upper eyelid in the standard fashion for Trabut surgery. (Fig. 1A, and Fig. 22 and 23 in yellow manual). A caliper is used to measure 3 mm ("C" in Fig. 2C) superior to the eyelash follicles on the conjunctiva across the width of the eyelid. The sharp point of the caliper or the scalpel blade can be used to make small scratches in the conjunctiva to delineate this position. This often corresponds to the scar or a portion of the scar from the original TT surgery ("scar" in Fig. 2B). A scalpel is used to make a tarsal incision along the marked position, beveled towards the eyelash follicles with care not to cut the follicles (the incision is the line between "B" and "D" in Fig. 2). Note that this beveled incision is in contrast to the typical Trabut incision that is made perpendicular to the plane of the upper evelid tarsus. Upon completion of the tarsal incision, sharp dissection between the scarred orbicularis and the scarred and thickened proximal tarsus is performed (Fig. 2D). White scar contributing to an eyelid contour abnormality is resected (Fig. 2E), and dissection is continued between the orbicularis and tarsus to the top of the tarsus (Fig. 2D). After dissection and release of the scar from the original TT surgery, the contour of both the beveled, distal fragment and the larger, proximal fragment should be normalized (Fig. 1B) The Trabut clamp and traction suture are removed.

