#### **Suturing**

If excess upper eyelid skin noted, a horizontal mattress suture (the "high" suture) is placed through the skin 10 mm above the lash line as the approximate position of the upper eyelid crease and through Muller's muscle just above the top the upper tarsus using 5-0 polyglactin 910 (Fig. 2F). Although, this suture is not tied until the end of the procedure, it is important to check that it is placed properly and does not undo the advancement when it is tightened. The relative position of the tarsal fragments is stabilized with horizontal mattress sutures as follows. Starting centrally, the suture is placed backhand from just above the lash line, through the distal fragment, and through the proximal tarsal fragment. The needle is repositioned in the standard forehand position, and the suture is advanced horizontally by 3 mm and is placed thorough the proximal tarsus, through the distal fragment, and exiting just above the lash line. At least 2 additional sutures are placed in the same fashion, nasal and temporal to the central suture. The 3 sutures can be placed for optimum contour if necessary. The "high" suture is then tied (Fig. 2F).

**Figure 1. Initial steps of BRAP.** A) Eversion of the upper eyelid with an eyelid contour abnormality over a Trabut plate. B) Upper eyelid after completion of the beveled incision, release and removal of the scar tissue, and normalization of the eyelid contour abnormality. C) Demonstration of ability to advance the proximal tarsal fragment, confirming adequate dissection.

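### The 12-month contour analysis makes no use of pre-operative contour, so it gives up some precision and cannot separate new abnormalities from repair of old ones

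*Combined protocol and SAP*

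**What the plan says.** Section 3.4 states secondary objective 1 as: "Determine whether the frequency of moderate/severe eyelid contour abnormalities at 12 months after surgery differs between the two procedures". Section 9.3 (Eyelid Contour Abnormalities) analyses a "dichotomous variable: presence or absence of moderate/severe contour abnormality at the final study" visit, using the field grade. The covariates are stated in one sentence: "We will adjust for first procedure performed (Trabut or BRAP) and severity of pre-operative trichiasis". The secondary contour analyses "will explore the relationship between procedure and the full range of eyelid contour abnormalities" from photographs graded centrally, and name no baseline contour term either.

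Other sections bear on who enters with an abnormality and what is measured before surgery:

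- Sections 5.1 and 5.2: eligibility requires post-operative trichiasis of an upper eyelid. The only exclusion is inability to consent.
- Section 6.1.2: the BRAP incision step removes scar that distorts the contour. The legend of Figure 1 describes "Eversion of the upper eyelid with an eyelid contour abnormality over a Trabut plate". The Trabut description in 6.1.1 has no such step.
- Section 3.3: BRAP "could ultimately be found to have higher rates of post-operative trichiasis or eyelid contour abnormalities", although preliminary data are said not to suggest it.
- Section 8.1: on the day of surgery, "The ocular exam will consist of a detailed evaluation of each eyelid". Contour is named only for follow-up visits. Each eyelid is photographed before surgery.
- Sections 3.5 and 10.3: contour grading is stated for post-operative visits.

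**The concern.** An eyelid counted as abnormal at 12 months may have arrived that way from its earlier surgery, or may have become so after the trial surgery. The procedures could differ on either path. BRAP is partly designed to repair an existing abnormality, while section 3.3 raises the possibility that it causes more. The planned analysis reports only the sum of the two.

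Two things are at stake. First, the baseline value of an outcome is often its strongest predictor, and leaving it out costs precision. The plan applies this principle to trichiasis, where the adjusted analysis uses baseline severity, but not to contour. Second, a near-zero difference could mean that the procedures behave alike, or that more new abnormalities are offset by more repair. A reader deciding whether to adopt BRAP would want to know which.

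**Working it through.** **Figures in the documents.** There is no sample size, power or control rate for contour. The 700 participants in section 9.2 are for trichiasis and reproduce: 35% vs 24.5%, two-sided 5%, 80% power, continuity-corrected, gives 316 per arm; 632/0.90 = 703 after rounding up. Nothing below depends on that figure. The one contour rate given, 45% after second surgery (section 3.2), is not stated to be moderate/severe or new. All contour rates below are therefore assumptions.

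**Eyelids per arm.** 936 − 186 = 750; less 10% loss = 675; about 338 per arm, taking one eyelid per participant.

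**1. Can opposite effects cancel?** Assume 30% of eyelids have moderate/severe abnormality before surgery.

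| | Persists if present | New if absent | 12-month rate |
|---|---|---|---|
| Trabut | 60% | 10% | 0.3×0.60 + 0.7×0.10 = 25.0% |
| BRAP | 35% | 20% | 0.3×0.35 + 0.7×0.20 = 24.5% |

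The unadjusted odds ratio is (0.245/0.755)/(0.25/0.75) = 0.97 (p = 0.88). With baseline contour as a covariate it is still 0.97 (p = 0.87). Split by baseline status, the odds ratios are:

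- new abnormality: (0.20/0.80)/(0.10/0.90) = 2.25;
- persistence: (0.35/0.65)/(0.60/0.40) = 0.36.

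Only the split, or the interaction, shows the pattern.

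**2. Precision of the split.** New: 0.7×338 ≈ 237 eyelids per arm; standard error √[(0.10×0.90 + 0.20×0.80)/237] = 3.2 points, so ±6.4 points. Persistence: 0.3×338 ≈ 101 per arm; √[(0.60×0.40 + 0.35×0.65)/101] = 6.8 points, so ±13.3 points.

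**3. Power gained from the covariate.** Logistic simulation, 338 independent eyelids per arm, true rates 25% vs 17%, baseline prevalence 20–45%. Power without the covariate is about 70–75%.

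| Baseline/12-month odds ratio | Power with covariate |
|---|---|
| 4 | 74–76% |
| 8 | 79–80% |
| 12 | 81–83% |

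The gain is about 3 points at an odds ratio of 4 and about 10 at 12. A second simulation (315 per arm, treatment odds ratio 0.6, 12-month risk 15% without baseline abnormality) brackets this:

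| Baseline prevalence | 12-month risk with baseline abnormality | Power without → with covariate |
|---|---|---|
| 30% | 30% | 58% → 60% |
| 30% | 60% | 58% → 70% |
| 30% | 80% | 42% → 61% |
| 45% | 80% | 45% → 67% |

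The last two rows imply an odds ratio of (0.80/0.20)/(0.15/0.85) ≈ 23, which is extreme.

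**4. Type I error.** In the second simulation with no treatment effect, 3.6% to 5.8% of tests rejected, with or without the covariate. Omitting it does not inflate error.

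**5. Chance imbalance.** At 30% prevalence the 95% range of the baseline difference is 1.96×√(2×0.3×0.7/338) = ±6.9 points. Carried to 12 months with the Trabut gap (0.60 − 0.10 = 0.50) this is 3.5 points. With the average of the Trabut and BRAP gaps, (0.50 + 0.15)/2 = 0.325, it is 2.2 points.

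**The case against.** The strongest reply is that the plan analyses exactly what the objective asks: the frequency of moderate/severe abnormality at 12 months. Contour status at one year matters to the patient however it arose, and correcting an old abnormality is a legitimate part of BRAP's effect. This stands. Only the word development in section 4.1 points towards counting new cases, which is too little to call the outcome wrong.

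Allocation is randomized 1:1, so prior abnormality is balanced in expectation, and chance imbalance is already covered by the standard error of the unadjusted comparison. This stands too. A reader might infer that the comparison is biased or its error rate inflated; the documents and the simulations do not support that.

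A reader might also infer that carried-over abnormality must dilute the effect. That holds only if the procedures leave old abnormality equally unchanged, and section 6.1.2 suggests otherwise. Nor do the documents show that BRAP causes more new abnormalities: the masking rates were chosen so that the two effects cancel.

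Finally, a baseline field grade may not exist. Contour grading is stated only for post-operative visits, examiners are standardized at the start of the 3-6 month visits, and the masked assessor stays away from the surgical site (6.2.1). This stands, and it is why the fix relies on photographs.

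None of this answers the remaining point: the plan does not use pre-operative contour anywhere, and neither procedure nor trichiasis severity substitutes for it.

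**Conclusion.** The contour analysis is consistent with secondary objective 1 and unbiased. It omits the baseline value of its own outcome in a population where all eyelids have had surgery and one procedure includes a step to repair existing abnormality. It therefore gives up precision, illustratively 3 to 10 points of power for baseline/12-month odds ratios of 4 to 12, with less gain if the association is weak. It also cannot tell fewer new abnormalities from more repair of old ones. Every size rests on assumed prevalence, persistence and association, and on independent eyelids, whereas the plan analyses eyes with generalized estimating equations. This is a worthwhile, inexpensive improvement to one secondary objective, not a flaw that invalidates it.

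**What to change.** In section 9.3, Eyelid Contour Abnormalities:

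1. Keep the planned 12-month outcome and all eyelids. Add pre-operative moderate/severe contour status (yes/no) as a covariate. Take it from one source for every eyelid: the pre-operative photographs of section 8.1, graded masked to arm under the central photographic grading already planned. Mixing field and photographic grades in one covariate should be avoided.
2. Pre-specify, as supporting results by arm, new moderate/severe abnormality among eyelids without it pre-operatively and persistence among eyelids with it, together with the arm-by-baseline interaction. Step 1 alone does not separate the two effects.

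The cost is grading the pre-operative photographs, which the plan does not clearly include now, plus one covariate, one table and a few lines of SAP text. The subset estimates will be less precise than the overall comparison and should be presented as supporting. The change should be fixed before any unmasked analysis, so that the split is not read as post hoc.
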